#### Noncutaneous Progression

PD includes new visceral sites of involvement or progression of visceral disease or the development of new or increasing tumor-associated edema or effusion lasting at least 1 week, which interferes with the subject’s normal activities. Progressive visceral disease, for measurable and evaluable disease, should be analogous to non-KS response criteria.

- 8.1.5 Recurrent disease is defined as the appearance of tumor following documentation of a complete remission.
- 8.1.6 Time to response is defined as time from the first dose of chemotherapy until documentation of first response.
- 8.1.7 Time to progression is defined as time from initiation of chemotherapy to documentation of first progression.
- 8.1.8 Response duration is defined as the time from first documentation of response to documentation of first progression.

## **9.0 RECORDS TO BE KEPT**

CRFs will be provided for each subject via the AMC AdvantageEDCSM Internet Data Entry System upon enrollment. Subjects must not be identified by name on any study documents. Data will be recorded on the CRFs using the unique subject identification number assigned at registration. Sample CRFs will be available on the AMC Operations Center website.

## **10.0 ROLE OF DATA MANAGEMENT**

### **10.1 CRF Instructions**

Instructions concerning the recording of study data on CRFs will be provided by the AMC Operations Center.

### **10.2 Data Quality**

It is the responsibility of the AMC Operations Center to assure the quality of data for the study. This role extends from protocol development to generation of the final study database.

## 11.0 STATISTICAL CONSIDERATIONS

### 11.1 Design and Sample Size

In Stage 1, three to six subjects were to be treated at each proposed dose levels to evaluate the MTD. In Stage 3, three to six initial subjects are to be treated at each proposed dose level to evaluate the potential MTD. Using the proposed dose escalation scheme, the probability of escalating to the next dose level, based on the true rate of DLT at the current dose, is given below:

**Table 6. Probability of Dose Escalation within Stage (Stage 1 & Stage 3)**

True Incidence of DLT	Probability of Escalating
10%	0.91
20%	0.71
30%	0.49
40%	0.31
50%	0.17
60%	0.08

Abbreviations: DLT = dose-limiting toxicity

Thus, if the true underlying proportion of DLTs is 20% at the current dose level, there is a high probability (0.71) of dose escalation to the next dose level. Conversely, if the true underlying proportion of DLTs is 50% at the current dose level, there is a low probability (0.17) of escalation to the next dose level.

In the Phase 2 portion of the study, Simon's 2-stage design is used to test the null hypothesis that the response rate (CR + PR) is  $\leq 10\%$  against the alternative that it is  $35\%$  at the one-sided 0.05 significance level with power of 0.90. Eleven subjects will be enrolled at the first dose level administered in Phase 2 (eg, 100 mg/dose BID) considering subjects from both the Phase 1 and Phase 2 portions of the study. If  $\leq$  one out of 11 subjects respond, the study will be stopped. If  $\geq$  two out of 11 subjects respond, the study will enroll 18-21 additional subjects in Stage 3. Assuming that the true response rate is  $\leq 10\%$ , the probability of stopping the trial at the end of Stage 2 is 0.697. However, if the true RR is  $\geq 35\%$ , then there is only a probability of 0.059 that the trial will be stopped erroneously in Stage 2.

Using the proposed dose escalation scheme from 100 mg/dose BID to 160 mg/dose TID, the probability of dose escalation based on the true rate of DLT at the lower dose, is given in Table 7 below:

**Table 7. Probability of Dose Escalation  
(100 mg/dose BID to 160 mg/dose TID)**

True Incidence of DLT	Probability of Escalating
10%	0.96
20%	0.82
30%	0.59
40%	0.35
50%	0.18
60%	0.08

Abbreviations: DLT = dose-limiting toxicity

Thus, if the true underlying proportion of DLTs is 20% at the 100 mg/dose BID dose level, there is a high probability (0.82) of dose escalation to the next dose level. Conversely, if the true underlying proportion of DLTs is 50% at the 100 mg/dose BID dose level, there is a low probability (0.18) of escalation to 160 mg/dose TID.

At the end of Stage 3, if  $\geq 6$  subjects respond, then the null hypothesis that the true response probability is  $\leq 10\%$  will be rejected, and further investigation of PTC299 in this patient population is warranted.

In Stage 3, a minimum of 12 patients will be treated at the maximally treated dose. If the underlying response rate is no greater than 10%, then the probability of observing 4 or more responses among 12 patients will be  $< 5\%$ . Thus, if there are 4 or more responses among 12 patients, it can be inferred that the response rate is  $> 10\%$ .

The minimum number of subjects to be entered in the study is **three** (i.e., if  $\geq$  two subjects experience DLT at the lowest dose level in Stage 1).

The maximum number of evaluable subjects to be enrolled in the study is **38** (i.e., 9 subjects have been enrolled into Stage 1, 8 subjects have been enrolled into Stage 2, and up to 21 subjects will be enrolled to Stage 3). Assuming that  $\sim 15\%$  of subjects will not be evaluable for response, we estimate that the maximum number of subjects in the study will be **44**.

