#### 1.2.5.5 Nonclinical Pharmacokinetics and Drug Metabolism

Nonclinical studies have demonstrated that PTC299 is orally bioavailable in mice, rats, and dogs. Plasma concentration-time data indicate rapid uptake of drug but a relative long mean time of maximum concentration ( $T_{\text{max}}$ ), generally ranging between 6 and 12 hours postdose. In all three species, the relationship between PTC299 dose and plasma exposure describes a “bell-shaped curve”, i.e., plasma exposures initially rise with dose to a peak and then decrease despite further increases in dose. These bell-shaped dose-exposure relationships are consistent with saturation of absorption and/or possible precipitation of drug within the gastrointestinal tract at higher dose levels. Maximal exposure in the dog is less than the maximal exposure in rodents. This difference is likely explained by more rapid PTC299 metabolism in the dog; the half-life ( $t_{1/2}$ ) values for PTC299 in dogs (3 to 8 hours) are shorter than in rodents (14 to 20 hours), and there is more rapid biotransformation of PTC299 in dogs than in rats, both in vitro in hepatocytes and in vivo.

The absorption, distribution, and excretion of PTC299 have been evaluated in vivo in a GLP study of oral administration of 50 mg/kg of  $^{14}\text{C}$ -labeled PTC299 in rats. In this study, absorbed radioactivity was rapidly distributed into the whole body with the  $T_{\text{max}}$  in blood and plasma occurring at 4 hours postdose in both sexes. The mean  $t_{1/2}$  in blood and plasma was long, at >60 hours for both sexes. Excluding the gastrointestinal tract, maximum concentration ( $C_{\text{max}}$ ) values in most tissues occurred at 6 to 12 hours postdose, with the highest values occurring in adipose tissues such as adrenal gland, brown fat, and liver. By 72 hours postdose, discernable residual radioactivity remained concentrated in fatty tissues in both sexes. Approximately 65 to 70% of the administered radioactivity was recovered in feces, with essentially no excretion in urine.

As expected given its low solubility, the in vitro protein binding of PTC299 in plasma is high (>99.5%) in all species tested (mouse, rat, dog, monkey,

and human). Given the similarities in protein binding across species, the data suggest that cross-species exposure comparisons do not need to be adjusted to take protein binding into account.

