When there is a dose modification, the subject should be notified of the change in dose and the appropriate clinic staff should instruct the subject about the revised number of study medication capsules to be used per dose according to the new dose level.

Clinical use of other anti-VEGF compounds (e.g., bevacizumab) can be associated with delayed wound healing. For this reason, subjects who require surgery or a deep invasive procedure should have PTC299 held for  $\geq 2$  weeks before the procedure, if possible, and PTC299 should be held for  $\geq 2$  weeks after the procedure, or until complete wound healing, to avoid the theoretical risk of impaired wound closure.

#### 5.3.5 Treatment in Phase 2

Once the safety profile at each dose level has been established based on first cycle DLTs in Phase 1, up to 21 additional subjects whose response to treatment can be evaluated will be enrolled in the Phase 2 portion of the study at the highest safely tolerated dose established in the Phase 1 portion to better define the safety, antitumor activity and biological activities of PTC299 at this dose level. In the Phase 2 portion of the study, Simon's 2-stage design will be used, as described in Section 11.1. Treatment will consist of 4 week cycles of therapy (56 or 84 doses) as described in Section 5.3.2. The maximum duration of treatment is 12, 4-week cycles. Definitions of DLT will be as described in Section 5.3.3. Study drug interruptions and dosage reductions will be managed as described in Sections 5.3.1 and 5.3.4.

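### The power of 0.90 in section 11.1 assumes one response rate across 100 mg BID and the higher Stage 3 doses, so it is not the power for the dose carried forward

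*Combined protocol and SAP*

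**What the plan says.** Section 11.1 of the combined protocol and SAP states that "Simon's 2-stage design is used to test the null hypothesis that the response rate (CR + PR) is" at most 10%, against 35%, "at the one-sided 0.05 significance level with power of 0.90".

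- **First stage.** "Eleven subjects will be enrolled at the first dose level administered in Phase 2 (eg, 100 mg/dose BID", counting subjects from the Phase 1 and Phase 2 portions together. If no more than "one out of 11 subjects respond, the study will be stopped". The stopping probability is given as 0.697 at a 10% rate and 0.059 at 35%.
- **Second stage.** If at least two of the 11 respond, "the study will enroll 18-21 additional subjects in Stage 3". Section 3.3.1 and the Schema plan these at 160 and 200 mg TID, with fallback to 120 mg TID or 100 mg BID if the higher levels are not tolerated.
- **Final rule.** The null is rejected if at least 6 subjects respond by the end of Stage 3. The text does not say in which subjects or at which dose they are counted, and its conclusion concerns the drug in this population.
- **Dose-specific rule.** After Table 7, 11.1 adds that 4 or more responders among 12 at the carried-forward dose would support a rate above 10%, with error below 5%. Section 11.2 gives a confidence interval width for those 12. No power is given.
- **Section 5.3.5.** Here the Simon design applies to up to 21 further subjects "enrolled in the Phase 2 portion of the study at the highest safely tolerated dose established in the Phase 1 portion", which is a single-dose description.

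**The concern.** A Simon design has one response probability throughout, and its power is the chance of rejecting when that probability equals the alternative. Here the first stage is given 200 mg a day (2 × 100) and the second is planned at 480 to 600 mg a day (3 × 160 to 3 × 200). Nowhere does the plan say that the response rate is assumed equal across these doses.

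If the rates differ, two things follow. A drug more active at the Stage 3 doses has a lower chance of success than 0.90, because it must first pass a gate at 100 mg BID. In the other direction, responders at 100 mg BID can supply most of the 6 needed, so that the null is rejected while the Stage 3 dose is no better than the null rate. Estimating the response rate is a primary objective (2.1.3), so a reader will want to know what a rejection says about the dose taken forward.

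**Working it through.** **Inputs.** Null rate 10%, alternative 35%, first stage n = 11, continue if at least 2 respond, reject if at least 6 respond (all 11.1). Second stage n₂ = 18 to 21 (11.1), which matches 3.3.1: 3 to 6 at 160 mg TID plus 15 at 200 mg TID.

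**Assumptions.** The 6 responders are counted over both stages. All Stage 3 subjects share one rate.

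**Formula.** With p_a the rate at 100 mg BID and p_b the rate in Stage 3:

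P(reject) = Σ over x = 2..11 of Bin(x; 11, p_a) × P(Bin(n₂, p_b) ≥ 6 − x).

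**The plan's own figures.** The stopping probability is P(X ≤ 1 of 11).
- At 10%: 0.9¹¹ + 11 × 0.1 × 0.9¹⁰ = 0.3138 + 0.3835 = 0.697, as stated.
- At 35%: 0.65¹¹ + 11 × 0.35 × 0.65¹⁰ = 0.0088 + 0.0518 = 0.061 (stated 0.059).

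A search for the optimal one-rate Simon design gives 1/11, then 5/27 (reject at 6 or more): power 0.908, type I error 0.0395, early stopping 0.697. That is where the 0.90 comes from, with 27 − 11 = 16 second-stage subjects.

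**Planned size, common rate, cut-off 6.** Power at 35% is 0.922 (n₂ = 18) to 0.932 (n₂ = 21). Type I error is 0.051 to 0.070.

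**Unequal rates, 35% in Stage 3:**

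| Rate at 100 mg BID | Stop before Stage 3 | P(reject), n₂ = 18 | P(reject), n₂ = 21 |
|---|---|---|---|
| 10% | 0.697 | 0.284 | 0.295 |
| 15% | 0.492 | 0.482 | 0.497 |
| 20% | 0.322 | 0.649 | 0.666 |
| 25% | 0.197 | 0.776 | 0.792 |
| 30% | 0.113 | 0.864 | 0.878 |
| 35% | 0.061 | 0.922 | 0.932 |

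The 20% row at n₂ = 18, term by term:
- x = 2: 0.2953 × 0.9217 = 0.2722
- x = 3: 0.2215 × 0.9764 = 0.2162
- x = 4: 0.1107 × 0.9954 = 0.1102
- x = 5: 0.0388 × 0.9996 = 0.0387
- x ≥ 6: 0.0117
- Sum: 0.649

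**The other direction.** With 35% at 100 mg BID and 10% in Stage 3, P(reject) is 0.511 (n₂ = 18) to 0.566 (n₂ = 21).

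**Dose-specific rule.** For 4 or more of 12: P(X ≥ 4) = 0.026 at 10% and 0.653 at 35%. Section 3.3.1 plans 15 subjects at that dose; keeping the cut-off of 4 gives 0.056 and 0.827.

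**The case against.** Several points on the other side are sound.

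- **Equal rates are not required.** A reader might infer that 0.90 holds only if both rates are 35%. That is too strong. With 35% at 100 mg BID, power is at least 0.90 for any Stage 3 rate of about 30% or more (n₂ = 18) or 26% or more (n₂ = 21). A pair of 40% and 25% gives 0.908 to 0.935. A common 35% is sufficient, not necessary. What remains is that if the 100 mg BID rate is 30% or less, the gate alone caps power at 0.887.
- **The stopping probabilities need no common rate.** 0.697 and 0.059 depend only on the 11 subjects at 100 mg BID.
- **The plan is not silent on the selected dose.** A reader might infer that it cannot say which dose is active. The 4-of-12 rule and the interval in 11.2 address this. What is missing is that rule's power, and which rule governs if the two disagree.
- **The pooled count is a reading.** If the 6 were counted in Stage 3 only, the 0.51–0.57 would fall to 0.006–0.014, but power at a common 35% would be only 0.606–0.751. The stated 0.90 fits the pooled reading.
- **Evidence for unequal rates is thin.** Section 1.2.5.5 reports that in animals "plasma exposures initially rise with dose to a peak and then decrease despite further increases in dose". A reader might infer that activity falls at the Stage 3 doses. But maximal exposures were at 100–120 mg/kg in rats and 30 mg/kg BID in dogs (1.2.5.6). Human exposure was roughly proportional to dose up to 103 mg TID, with troughs above target at every dose (1.2.6.2). Unequal rates are possible; the documents do not show them to be likely.
- **Fallback.** If Stage 3 returns to 100 mg BID, the two stages partly share a dose.
- **Timing.** Sections 3.3.1 and 11.1 say the Stage 2 subjects have been enrolled, so new wording cannot change enrolment for the gate.

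**Conclusion.** The concern holds in a limited form. The 0.90 is a property of a one-rate design, while the plan applies it to a first stage at 100 mg BID and a second stage planned at higher TID doses. It is not the power for the dose carried forward. With 35% in Stage 3, the chance of rejection runs from 0.28–0.30 to 0.78–0.79 as the 100 mg BID rate goes from 10% to 25%, and is 0.92–0.93 at a common 35%. A pooled rejection therefore supports activity at one or more of the doses studied and no more. The rule that does address the selected dose has power 0.653 at 35%, which the plan does not state.

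These figures rest on counting responders over both stages, one response rate for all Stage 3 subjects, and no fallback to 100 mg BID. Separately, 5.3.5 describes a single-dose Simon design, and 11.1 and 3.3.1 do not. With the 100 mg BID subjects already enrolled, the point bears mainly on the final conclusion rather than on the interim gate.

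**What to change.** In section 11.1:

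1. State that the power assumes a common response rate at 100 mg BID and the Stage 3 doses. Recompute power and type I error for the planned 18–21 second-stage subjects (0.92–0.93 and 0.051–0.070 with the cut-off of 6), and add a table for unequal rates.
2. Say that the 6 responders are counted over both stages, and that rejection supports only activity at one or more of the doses studied.
3. Rest the conclusion for the selected dose on the existing dose-specific rule and an exact interval from subjects treated at that dose. State the rule's power: 0.653 for 4 of 12. If the rule is applied to the planned 15, say so and give its properties (with a cut-off of 4, power 0.827 and type I error 0.056).
4. Reconcile 5.3.5 with 11.1 and 3.3.1 on which doses the Simon design covers.

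The cost is protocol and SAP wording. No extra subjects or procedures are needed. The price is a less favourable statement: type I error slightly above 0.05 unless the cut-off is revisited, and power for the selected dose below 0.90.

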### **3.3 Number of Subjects to be Enrolled**

- 3.3.1 Three to 38 evaluable subjects will be enrolled. In Stage 1, three successive cohorts of three subjects have been enrolled at each of the following dose levels: 40 mg/dose BID, 80 mg/dose BID, and 100 mg/dose BID. An additional eight subjects have been enrolled in Stage 2 at the highest safely tolerated dose (e.g., 100 mg/dose BID) established in Stage 1 to better define the safety, antitumor activity, and biological activities of PTC299 at this dose level. Dose escalation will continue in Stage 3 for two additional successive cohorts of 3 to 6 subjects at the following dose levels: 160 mg/dose TID and 200 mg/dose TID. Once the safety profile at each level has been established based on first cycle dose-limiting toxicities (DLTs), an additional 9 to 12 subjects will be enrolled at the highest safely tolerated dose (e.g., 200 mg/dose TID) for a total number of 15 subjects at this dose level. If the dose level of 200 mg/dose TID is not well tolerated (i.e.,  $\geq 2/6$  subjects experience a first-cycle DLT), an additional 9 to 12 subjects will be enrolled at the dose level of 160 mg/dose TID for a

total number of 15 subjects at the MTD. If the dose level of 160 mg/dose TID is not well tolerated in the initial cohort (e.g.,  $\geq 2/3$  or  $\geq 2/6$  subjects experience a first-cycle DLT), 3 to 15 subjects will be enrolled at the dose level of 120 mg/dose TID. If the dose level of 120 mg/dose TID is not well tolerated (e.g.,  $\geq 2/3$  or  $\geq 2/6$  subjects experience a first-cycle DLT), a total of 9 to 15 subjects will be enrolled at the 100 mg/dose BID dose level in Stage 3. Collectively, up to 21 patients will be enrolled in Stage 3.

- 3.3.2 Estimated accrual rate: four subjects per month.

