### 5.3.2 Dose Escalation Rules and Definition of MTD

In Stage 1, each subject will be assigned to Dose Level 1 (40 mg/dose BID), Dose Level 2 (80 mg/dose BID), or Dose Level 3 (100 mg/dose BID) sequentially according to the dose level being explored at the time of subject enrollment. A Dose Level -1 (20 mg/dose BID) is provided in case a subject assigned to Dose Level 1 (40 mg/dose BID) requires dose reduction. In Stage 2, 8 subjects were enrolled at the Stage 1 MTD, Dose Level 2 (100 mg/dose BID). In Stage 3, each subject will be assigned to Dose Level 6 (160 mg/dose TID), or Dose Level 7 (200 mg/dose TID) sequentially according to the dose level being explored at the time of subject enrollment. Dose Level 5 (120 mg/dose TID) is provided in case a subject assigned to Dose Level 6 (160 mg/dose TID) requires dose reduction. Dose Level 4 (100 mg/dose BID) is provided in case a subject assigned to dose Level 5 (120 mg/dose TID) requires dose reduction.

During the study, dose escalation will depend on evaluations of safety in cycle 1 of therapy. The following dose escalation rules will be employed:

- Three subjects will be studied at the first dose level. If none of these three subjects experience DLT during cycle 1, then the dose will be escalated to the next higher level in the three subsequent subjects.
- If one of three subjects experiences DLT at the current dose during cycle 1, then three more subjects will be accrued at the same dose. If none of these three additional subjects experience DLT during cycle 1, then the dose will be escalated in subsequent subjects. If one or more of the three additional subjects experiences DLT in the first cycle, the MTD has been exceeded and three more subjects will be treated at the next lower dose (if only three subjects were previously treated at that prior dose).
- If two or more subjects experience DLT in the first cycle, then the MTD has been exceeded and three more subjects will be treated at the next lower dose level (if only three subjects were previously treated at that prior dose).
- No intrasubject dose escalations in subsequent cycles of therapy will be permitted.

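### Under the natural cumulative reading, the cutoff of six responders fits 27 subjects, but the plan enrols 29 to 32, so the one-sided error reaches 0.070 rather than 0.05; the plan also does not say which subjects count

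*Combined protocol and SAP*

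**What the plan says.** Section 11.1 (the text after Table 6) describes the phase 2 efficacy test as a Simon two-stage design, with a null response rate (complete plus partial) of at most 10% and an alternative of 35%, "at the one-sided 0.05 significance level with power of 0.90". For the first stage, "Eleven subjects will be enrolled at the first dose level administered in Phase 2", counting subjects from both the phase 1 and phase 2 portions. The trial stops if one or none of the 11 respond. With two or more, "the study will enroll 18-21 additional subjects in Stage 3". At the end of Stage 3, if at least six "subjects respond, then the null hypothesis that the true response probability is" 10% or less is to be rejected and the drug is judged worth studying further. The stated probabilities of stopping early are 0.697 at a 10% rate and 0.059 at 35%.

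Section 3.3.1 gives the make-up of Stage 3: "Dose escalation will continue in Stage 3 for two additional successive cohorts of 3 to 6 subjects", then an expansion at the chosen dose "for a total number of 15 subjects at this dose level", with at most 21 in the stage. Under Section 5.3.2 a cohort starts with three; after one dose-limiting toxicity among them, "then three more subjects will be accrued at the same dose". Section 5.3.5 speaks of "up to 21 additional subjects whose response to treatment can be evaluated will be enrolled in the Phase 2 portion of the study". Section 11.1 also says that at least 12 subjects will be treated at the top dose.

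**The concern.** A Simon cutoff is calibrated to a particular total sample size. Here six responders is given without a total, and the second stage is a range rather than a number. Adding subjects while holding the cutoff fixed makes it easier to reach by chance, so the error rate rises with every extra subject.

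The count decides whether the trial is declared positive. If the level is higher than stated, a result such as 6 of 32 would be reported as significant at 0.05 when the rule does not work at that level. If the denominator stays open, two analysts could also reach opposite conclusions from the same data.

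**Working it through.** **Inputs (Section 11.1 unless noted).** Null rate 0.10, alternative 0.35; 11 first-stage subjects; continue with 2 or more responders; n₂ = 18 to 21 second-stage subjects; reject with 6 or more. Assumption: one response rate p applies at every dose.

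**1. The plan's own stopping probabilities.** P(at most 1 of 11) is 0.697 at p = 0.10, as stated. At p = 0.35 it is 0.061, against the stated 0.059, a small difference. The first stage is therefore the one the plan intended.

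**2. Where the cutoff comes from.** An exhaustive search of two-stage designs with level at most 0.05 and power at least 0.90 finds the smallest expected sample size under the null (15.84) at: stop on at most 1 of 11, then reject on at least 6 of 27. Its level is 0.0395 and its power 0.908. It matches the plan's 11, its stopping rule, its 0.697 and its cutoff of 6. Only the second stage differs: 27 − 11 = 16, against 18 to 21. The total of 27 is derived here; it does not appear in the plan.

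**3. Error at the planned size, cumulative count.** The rejection probability is

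Σ (x = 2 to 11) P(Bin(11, p) = x) × P(Bin(n₂, p) ≥ 6 − x).

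For p = 0.10 and n₂ = 21 (total 32):

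| First-stage responders | Probability | Chance of reaching 6 | Product |
|---|---|---|---|
| 2 | 0.2131 | 0.1520 | 0.0324 |
| 3 | 0.0710 | 0.3516 | 0.0250 |
| 4 | 0.0158 | 0.6353 | 0.0100 |
| 5 | 0.0025 | 0.8906 | 0.0022 |
| 6 or more | 0.0003 | 1 | 0.0003 |

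The products sum to 0.0699. The same formula for other totals, and for a cutoff of 7, gives:

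| Total | Level, ≥6 | Power, ≥6 | Level, ≥7 | Power, ≥7 |
|---|---|---|---|---|
| 26 | 0.034 | 0.898 | 0.011 | 0.834 |
| 27 | 0.040 | 0.908 | 0.013 | 0.856 |
| 28 | 0.045 | 0.916 | 0.016 | 0.874 |
| 29 | 0.051 | 0.922 | 0.019 | 0.889 |
| 30 | 0.057 | 0.927 | 0.022 | 0.900 |
| 31 | 0.063 | 0.930 | 0.026 | 0.910 |
| 32 | 0.070 | 0.932 | 0.029 | 0.917 |

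With a cutoff of 6, both targets are strictly met only at 27 and 28.

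**4. How a total of 32 arises.** The dose not chosen for expansion has 3 or 6 subjects and the chosen dose has 15, so a full Stage 3 is 3 + 15 = 18 or 6 + 15 = 21. The chance that a given first cohort of three has exactly one toxicity, and so expands to six, is 3q(1 − q)². That is 0.24, 0.38 and 0.44 at true toxicity rates q of 10%, 20% and 30%.

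**5. Other ways to count the six.**

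- Stage 3 subjects only, after passing the first stage: level 0.002 to 0.004, power 0.61 to 0.75.
- The 11 plus 12 to 15 top-dose subjects (totals 23 to 26): level 0.021 to 0.034, power 0.846 to 0.898.
- All subjects, 9 + 8 + 18 to 21 = 35 to 38: level 0.090 to 0.111, power 0.94.

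**The case against.** The level of 0.070 is conditional: it needs the cumulative reading and a Stage 3 of 21. The 11 plus 15 top-dose subjects make 26, where the level is 0.034 and the power 0.898, which is 0.90 to two decimals. That is close to what the plan claims. However, Section 11.1 makes the second stage 18 to 21 subjects, not 15, and guarantees only 12 at the top dose, where power falls to 0.846. This reading does not secure the stated figures.

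The excess is also small in practice. Full accrual gives 29 or 32; totals of 30 and 31 need incomplete or non-evaluable accrual. The cohort-expansion chance in step 4 is not the chance of reaching 32, because a later failure at the higher dose can return the expansion to the lower one. Following the escalation rules through, with equal toxicity rates at both Stage 3 levels and assuming 15 subjects at the fallback level if the first one fails, a Stage 3 of 21 has probability about 0.29 at a 10% rate and 0.46 at 20%. The averaged level is then 0.051 + 0.29 × 0.019 = 0.056, or 0.051 + 0.46 × 0.019 = 0.060. This is fair, and it fixes the scale of the problem.

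Finally, the response rate will also be reported with a 95% confidence interval (Section 11.2), and Section 11.1 has a separate rule of 4 or more responses among 12 at the top dose. Neither replaces the six-responder rule, to which Section 11.1 ties rejection of the null. Under the cumulative reading the 4-of-12 rule adds no further error: 2 first-stage responders plus 4 in Stage 3 already make 6.

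**Conclusion.** The concern holds. The cutoff of six is that of a 27-subject Simon optimal design, and the plan applies it to 29 to 32. Under the cumulative reading and a common response rate, the one-sided level is 0.051 to 0.070 instead of 0.05. The excess is 0.1 percentage points at 29 and 0.7 to 2.0 points at 30 to 32. Power is not harmed (0.922 to 0.932). The missing denominator is a defect under any reading: across the candidate counts the level runs from 0.002 to 0.111 and power from 0.61 to 0.94, and none delivers the stated pair throughout its planned range. This should be fixed before the final analysis, but it does not undermine the trial.

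**What to change.** State in Section 11.1 that responders are counted among the 11 first-stage subjects plus all evaluable Stage 3 subjects. Then adopt one of the following:

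- **(a)** Keep the cutoff of 6 and restate the level as 0.051 to 0.070 for totals of 29 to 32, with power 0.922 to 0.932.
- **(b)** Require 7 responders for totals of 30 to 32 (level 0.022 to 0.029, power 0.900 to 0.917) and keep 6 for totals of 26 to 29 (level 0.034 to 0.051, power 0.898 to 0.922). The low end, 26, is 11 plus the minimum 12 at the top dose plus 3 at the other level. The 0.051 at 29 should be stated openly.

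Applying the cutoff of 6 to a prespecified first 27 or 28 subjects would also meet both targets, but it leaves the last subjects out of the test.

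Stages 1 and 2 are already enrolled, so first-stage responses may be known. The choice should be made without reference to them, and that should be documented; if it cannot be, default to (a).

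The cost is a few sentences and no extra patients. Option (a) means a less favourable stated level. Option (b) gives up 2.6, 2.0 and 1.6 points of power at 30, 31 and 32 subjects (0.927 to 0.900, 0.930 to 0.910 and 0.932 to 0.917; differences taken before rounding).
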